6.4 Performance Measurements

Charlson Co-morbidity Index³⁸

This is a validated age-comorbidity index used to estimate relative risk of death from prognostic clinical covariates, and useful in studies with 1 to 2 year follow up.

Karnofsky Performance Status Scale^{39 40}

This validated scale incorporates the components of physical activity, work and self care of patients.

6.5 Health Economic Assessments

In addition to the EQ5D

Health Service Use Questionnaire

The Health Service Use Questionnaire is designed to measure the level of health service resource use. Respondents are asked to recall the amount of use they have made of the specified services over the previous 6 months.

[figure not shown]
Table 1: HOT Main Trial - Patient Assessment Schedule

Assessment	Months After Recruitment ¹							
	Baseline	3	6	12	18	24		
Clinical	Clinic	Home	Clinic	Clinic	Clinic	Clinic		
Age, Sex, Aetiology, Height	X							
Weight	Х		Х	X	Х	Х		
Current Medication	Х	X	Х	X	Х	Х		
Resting Pulse Rate & Blood Pressure, Respiratory Rate	Х	X	Х	X	Х	Х		
Assessment of Peripheral Oedema & Lung Crackles	Х		X	Х	X	Х		
ECG	Х		X	Х	X	Х		
Blood Test - BCP, FBC (Standard Biochem' & Haem')	Х		X	Х	X	Х		
Blood Test – Nt pro BNP	X ²	X	X	X	X	X		
Spirometry	X			Х		Х		
Echocardiogram	X			X		X		
6 Minute Walk Test & Pre/Post O2 Saturation	X		X	X	X	X		
Overnight Sleep Test (if locally accessible)	X		X	X	X	X		
Charlson Co-Morbidity Index	X		X	X	X	X		
Karnofsky Performance Score	X	X	X	X	X	X		
Quality of Life								
Minnesota Living with Heart Failure Questionnaire (MLWHF)	X	X	X	X	X	X		
Numerical Rating Scale - Breathlessness (NRS)	X	X	X	X	X	X		
Hospital Anxiety & Depression Scale (HADS)	X		X	X	X	X		
Epworth Sleep Score	X	X	X	X	X	X		
Health Economics								
EuroQoL	X		X	X	X	X		
Health Service Use Questionnaire (not all questions)	X		X	X	X	X		

.

¹ It is intended that all patients will participate in the trial for 12 months, or until the last patient has completed, up to a maximum of 24 months. Assessments occur at 3 months (+/- 7 days), or at 6 monthly time points (+/- 14 days) thereafter. At trial end summary data on mortality and hospitalisations will be collected from clinical records for all participants.

² Investigations in 'blue' are trial investigations. Those in 'black' are routinely used within clinics for this patient group.

7. Economic Analysis and Modelling

Systematic reviews will be conducted to identify existing studies providing information on the costs, resource use and health outcomes associated with CHF and HOT. The analysis will be undertaken from the cost perspective of the NHS and using methods outlined in the National Institute of Health and Clinical Excellence (NICE) methods quide.xii

The cost-effectiveness results will be expressed in terms of the incremental health service costs and quality adjusted life years (QALYs) gained. Where appropriate, separate analyses will be conducted for patient sub-groups with different levels of baseline risk or expected benefit. The primary analysis will be the cost per QALY gained over one year of treatment with NOT or LTOT relative to best medical therapy.

To explore more long-term outcomes a probabilistic decision-analytic model will be constructed to represent the natural history of CHF with which the cost-effectiveness of NOT and LTOT can be evaluated relative each other and to best medical therapy over a longer time horizon. The model will track the resource use and costs as well as the quality of life and health outcomes for patients with CHF. Prognostic information collected during the trial will be used in combination with published studies to link changes in severity of disease at one year to long term outcomes. Structural and modelling uncertainty will be fully explored using scenario analysis. The decision-analytic model will follow the guidelines for good modelling practice.

8. Statistical Considerations

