Home oxygen therapy (HOT), an expensive treatment which is potentially burdensome for patients and carers, is often prescribed for patients with chronic heart failure, although it is unknown whether it is of benefit in the medium to long-term with regard to symptoms, severity of CHF, hospitalisation or survival. Also unknown, assuming oxygen is of benefit, is how it should be administered; short burst oxygen therapy (SBOT), nocturnal (NOT) or long-term (LTOT). In addition to the concern that there is no proven benefit from oxygen, some reports suggest that hyperoxia leads to clinically significant adverse haemodynamic effects such as increased vascular resistance, left ventricular filling pressure, blood pressure and reduced cardiac output due to the formation of oxygen free radicals.¹²

There are only a few, small, unpowered studies looking at the effect of short term SBOT on breathlessness and exercise tolerance in a variety of conditions. Those trials that randomised patients did not confirm benefit. A large observational study of patients with breathlessness of varying aetiology concluded that oxygen therapy was of no benefit for symptom relief in the absence of hypoxaemia, a finding echoed in a Cochrane review. A recent double blind placebo controlled study confirmed that oxygen was no better than placebo for the relief of intractable breathlessness in study participants, a few of whom had CHF.

The benefits for mortality and morbidity of LTOT in patients with chronic obstructive pulmonary disease and hypoxia are well established,¹⁷ but dependent upon good compliance. One study has suggested that there is less than 30% compliance with prescribed therapy.¹⁸ LTOT (>15 hours per day) has not been studied in patients with left ventricular dysfunction or CHF. The criteria which should be used to assess suitability of LTOT in patients with CHF, let alone benefit in terms of survival, severity of disease or symptomatology is unknown. It is also unknown whether CHF patients would tolerate the intervention which would be more intrusive than NOT alone.

NOT has been studied in small randomised trials in patients with CHF with a maximum follow-up of 3 months¹⁹ ²⁰ ²¹ ²² ²³ and appears to reduce CSA and nocturnal sympathetic activity; evidence of improvement either of cardiac function or symptoms is inconsistent.

3. Aims and Objectives

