4.1 Design

This is a phase 3, prospective, multi-centre, randomized, parallel-group, controlled trial in patients with stable NYHA Grade III/IV heart failure receiving optimal medical therapy. 450 eligible patients will be allocated by block randomisation 1:1:1 to one of the three limbs of the study, to receive for a period of at least one year, either (a) best medical therapy without home oxygen treatment; (b) best medical therapy with Long Term home Oxygen Therapy (daytime LTOT, for at least 15 hours per day); or (c) nocturnal oxygen therapy (NOT, at least 8 hours per night).

Although the primary end-point of the study is one-year quality of life, data are also to be collected at 3 months during a home visit by the study nurse in order to detect any transient change in quality of life that is lost later. All patients will be asked to continue in the trial with 6-monthly assessments until the last patient recruited has finished one year's participation in the trial. This allows the trial to address quality of life changes and cost effectiveness (the primary outcome), and also to make a provisional assessment of the effect on clinical outcomes, and associated cost effectiveness.

HOT Trial Summary Flow Chart

Patient identification from database, heart failure nurse case list, or treating physician

↓

Eligibility Criteria Fulfilled

↓

Informed Consent

↓

Pandomisation to one of 3 Groun

Simple Randomisation to one of 3 Groups

Baseline Data Collection

Medical Therapy + NOT Medical Therapy + LTOT

Assessments at Baseline, 3 months & 6 monthly thereafter for 1 year, or until the last patient has completed, up to a maximum of 2 years.

Study End with Assessment of Patient for Further NHS Oxygen Therapy

There will be a nested, qualitative, single centre sub-study involving semi-structured interviews with a purposive sample of patients in each arm of the study to explore the views and experience of participants and their carers regarding oxygen therapy. An entirely separate, single centre sub-study will assess the acute effect of oxygen on haemodynamics in patients with CHF.

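### The primary one-year cost per QALY compares each oxygen regimen only with best medical therapy, which cannot identify the cost-effective choice among three alternatives

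*Protocol*

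**What the plan says.** Section 4.1 of the Protocol sets up three alternatives: "450 eligible patients will be allocated by block randomisation 1:1:1 to one of the three limbs of the study". Section 7 then does four things.

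- It refers in general terms to a methods source, "using methods outlined in the National Institute of Health and Clinical Excellence (NICE) methods" guide.
- It says how results are expressed: "The cost-effectiveness results will be expressed in terms of the incremental health service costs and quality adjusted life years (QALYs) gained". That sentence names no comparator.
- It fixes the primary analysis: "The primary analysis will be the cost per QALY gained over one year of treatment with NOT or LTOT relative to best medical therapy". The only comparator named is best medical therapy.
- It adds a second strand: "To explore more long-term outcomes a probabilistic decision-analytic model will be constructed". With this model, "the cost-effectiveness of NOT and LTOT can be evaluated relative each other and to best medical therapy over a longer time horizon".

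The comparison between the two oxygen regimens is therefore planned, but it is stated only for the long-term model. Section 2 lists the choice of regimen among the open questions: "Also unknown, assuming oxygen is of benefit, is how it should be administered". Cost-effectiveness is secondary endpoint 9 in section 3.5.

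**The concern.** A payer can provide a given patient with only one of best medical therapy, NOT or LTOT. Which one is good value depends on what each step up in cost buys over the next less costly option worth considering. Two ratios against best medical therapy do not answer that. An option that costs more than another and yields no more QALYs still has a finite ratio against best medical therapy. So does an option that is extendedly dominated, meaning that the next step up buys QALYs at a lower price than the step to it.

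At stake is the one-year result, the economic analysis closest to the randomised data and the one labelled primary. It could leave the choice between regimens unanswered, or suggest an answer that the trial's own costs and QALYs do not support.

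**Working it through.** **Inputs.** Section 7 contains no cost, utility, QALY or willingness-to-pay figure, so there is no economic figure to reproduce. Every cost, QALY and threshold below is an assumption. BMT stands for best medical therapy, and increments are over BMT at one year.

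**General form.** Let r be the cost per QALY of NOT against BMT. Let LTOT's extra cost be c times that of NOT, and its QALY gain q times, with all increments over BMT positive.

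- Reported by the rule as written: LTOT against BMT = r × c/q.
- Relevant to the choice when c > 1 and q > 1: LTOT against NOT = r × (c − 1)/(q − 1).

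The second exceeds the first exactly when q(c − 1) > c(q − 1), that is, when c > q. There are three cases with LTOT the dearer option:

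- q ≤ 1: NOT dominates LTOT, yet the rule still reports the finite ratio r × c/q.
- c > q > 1: the reported ratio understates the price of moving from NOT to LTOT.
- q > c: the reported ratio overstates that price, and NOT is extendedly dominated, which the rule does not show.

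Multiples of r for some assumed pairs:

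| c | q | Reported c/q | Against NOT (c − 1)/(q − 1) |
|---|---|---|---|
| 1.5 | 1.1 | 1.36 | 5 |
| 1.5 | 1.2 | 1.25 | 2.5 |
| 1.25 | 1.2 | 1.04 | 1.25 |
| 1.05 | 1.1 | 0.95 | 0.5 |

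**Illustration 1.** NOT: +500 cost, +0.040 QALY, so 500/0.040 = 12,500 per QALY. At an assumed threshold of 20,000, NOT's net benefit is 20,000 × 0.040 − 500 = 300. LTOT: +800 cost, with its QALY gain varied.

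| LTOT gain | LTOT against BMT | LTOT against NOT | LTOT net benefit |
|---|---|---|---|
| 0.035 | 22,857 | dominated | −100 |
| 0.040 | 20,000 | dominated | 0 |
| 0.045 | 17,778 | 300/0.005 = 60,000 | 100 |
| 0.050 | 16,000 | 300/0.010 = 30,000 | 200 |
| 0.055 | 14,545 | 300/0.015 = 20,000 | 300 |
| 0.060 | 13,333 | 300/0.020 = 15,000 | 400 |

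Two things follow.

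- Asking only whether a ratio is acceptable passes LTOT from a gain of 0.040 upward, although its net benefit stays below NOT's until 0.055. At an assumed 25,000 per QALY even the dominated row at 0.035 passes: 25,000 × 0.035 − 800 = +75, against 25,000 × 0.040 − 500 = 500 for NOT.
- Choosing the lower of the two ratios fails as well. NOT's 12,500 is lower in every row, yet at 0.060 LTOT has the higher net benefit (400 against 300).

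**Illustration 2, the other direction.** Keep NOT as above and take c = 1.05, q = 1.1, so LTOT is +525 and +0.044 QALY. Against BMT: 525/0.044 = 11,932. Against NOT: 25/0.004 = 6,250. LTOT's net benefit at 20,000 is 880 − 525 = 355, against 300 for NOT. The step to LTOT costs less per QALY (6,250) than the step to NOT (12,500), so NOT is extendedly dominated. The rule as written still reports it at 12,500 as a free-standing option.

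**The case against.** The case on the other side has real content.

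- **The comparison of regimens is already planned.** True, in the long-term model. That model is introduced as exploratory and combines trial information with published studies. It does not replace the one-year comparison of the randomised arms.
- **Section 7 states no decision rule or threshold, and when c > q the reader sees NOT with the better ratio.** Both correct. In the dominated case, too, NOT shows the lower ratio. But the order of the two ratios does not settle the choice, as the row at 0.060 shows.
- **The contrast can be recovered by subtraction,** because incremental costs and QALYs will be reported. This stands for the point estimate. The two ratios and their intervals do not by themselves give its uncertainty or the probability that each option is best.
- **The NICE methods guide is cited.** Its content is not in the documents, so it cannot be said what it would require here. A general citation does not override the comparator specifically named.
- **Ranking and dominance rules belong in an analysis plan.** Their absence alone would be no finding. The point rests on the comparator, which the Protocol fixes.
- **The trial was sized for two comparisons with best medical therapy (section 8.1).** That governs significance tests on the Minnesota score. It does not bar estimating increments or net benefit.

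A reader might infer that no economic comparison of NOT with LTOT is planned, that the plan is tilted towards LTOT, or that its ratio will be understated several-fold. The documents support none of these. The comparison exists in the model, the direction depends on unknown costs and QALYs, and both regimens use home concentrators (section 6.1), so their costs may be close.

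**Conclusion.** The concern holds for the primary one-year economic analysis. As worded, it compares each oxygen regimen with best medical therapy alone, and two such ratios cannot identify the cost-effective option among three. This is a property of the rule and does not depend on the assumed figures.

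Its practical size cannot be determined from the Protocol. In the illustrations the ratio against NOT ranges from about half the reported ratio (6,250 against 11,932) to more than three times it (60,000 against 17,778), and dominated options also receive finite ratios. These show the possible behaviour and are not predictions for this trial. A conflict between the one-year result and the long-term model is likewise possible but not certain, since the model has a longer horizon and draws on published data as well. The wording should be changed; the flaw does not undermine the trial's design or its clinical primary endpoint.

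**What to change.** Replace the sentence in section 7 that defines the primary economic analysis with text such as:

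> The primary economic analysis will be a fully incremental comparison of best medical therapy, NOT and LTOT over one year. Options will be ranked by mean cost, dominated and extendedly dominated options removed, and the cost per QALY of each remaining option calculated against the next less costly one. Expected net benefit, and the probability that each of the three options is the most cost-effective, will also be reported. Ratios for NOT and LTOT against best medical therapy will be given as supporting results.

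The cost is one sentence and a little more analysis. Table 1 already schedules the EQ-5D and the health service use questionnaire at baseline, 6 and 12 months, so no further patients or assessments are needed. The downside is small: the NOT-versus-LTOT ratio will be imprecise and should be reported with its uncertainty.

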8.1 Sample Size

Study power is difficult to calculate. The Minnesota Living with Heart Failure scale is the most widespread tool for assessing quality of life in patients with chronic heart failure. An improvement of 5 is sometimes taken to be a minimum clinically important difference, but others have suggested that a change of one standard error around the mean score is needed (around 6 or 7, depending upon the population studied). There are no studies of long term oxygen therapy to help guide us. The MIRALCE trial of biventricular pacing was powered for a 13 point improvement in MLWHF, and found a difference of 9 between treatment groups. The CARE-HF study of biventricular pacing found an improvement of 10.6 with intervention. In the absence of hard data on which to base study size, we have taken a Minnesota score of 10 as an arbitrary indicator of the minimum improvement necessary to justify the cost and inconvenience of oxygen therapy for patients.

For a 10 point difference in MLWHF score, and with a standard deviation of 25 and assuming a P of 0.025 (for two comparisons) and 80% power we will need 119 in each group or 150 in each group if we assume a 20% attrition rate.

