8.2 Statistical Analysis

The clinical trial will be reported according to the CONSORT guidelines for clinical trials. Baseline data (sex, age, diagnosis distributions etc.) will be presented in tabular form. Data will be summarised using descriptive statistics. Data will be analysed according to intention-to-treat criteria. A secondary analysis will be an on-treatment analysis. A secondary analysis will be by baseline mean nocturnal oxygen saturation. Whilst patients may, of course, withdraw from treatment at any time, they will all be encouraged to remain under follow up.

Statistical comparisons will compare the measurements of primary and secondary outcomes between the groups. For continuous data, ANCOVA will be used to compare the groups, whilst controlling for the baseline measure and confounding factors. KM and Cox regression will be used for time to event data such as mortality. All analyses will be undertaken on SPSS.

Missing data is a well recognised problem in longitudinal studies, particularly with patients with advanced disease. We will handle missing data by using the extreme values. By making the assumption that the missing value is the worst it could be for the intervention and the best it could be for the standard care group (best medical therapy). If there remains a statistically significant difference between treatments then one can be sure that the results are robust. Other techniques that we have considered involve building a regression equation to predict the value of the missing data from the baseline characteristics from patients with no missing values or the use of other imputation techniques such as mean values. Expert statistical advice will be provided by [name].

9. Pharmacovigilance

The collection and reporting of data on adverse events and serious adverse events will be in accordance with ICH GCP and the Research Governance Framework 2005.

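### Naming Holm's procedure for the two primary comparisons would add power if both oxygen regimens work, at the same sample size and within the 5% familywise error; this is an inexpensive improvement, not an error

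*Protocol*

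**What the plan says.** Section 8.1 calculates the sample size "For a 10 point difference in MLWHF score", "with a standard deviation of 25", and "assuming a P of 0.025 (for two comparisons) and 80% power we will need 119 in each group". The 119 is raised to 150 for 20% attrition. The 0.025 is the only allowance for multiplicity in the protocol.

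Section 4.1 sets the allocation: "450 eligible patients will be allocated by block randomisation 1:1:1 to one of the three limbs of the study". Section 8.1 does not name the two comparisons. The primary research question in section 3.1 sets each oxygen regimen against best medical therapy, so they are taken here as LTOT versus best medical therapy and NOT versus best medical therapy.

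Section 8.2 states: "Statistical comparisons will compare the measurements of primary and secondary outcomes between the groups". It specifies ANCOVA with adjustment for baseline and refers to statistical significance when it discusses missing data. It gives no significance level, testing order or multiplicity procedure. The SAP is not at hand.

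**The concern.** If each comparison is tested against a fixed 0.025, the second is held to that threshold even when the first has already succeeded. Familywise control does not require this. Once one null hypothesis has been rejected, only one remains, and it can be tested at the full 5%.

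The second comparison matters in this trial. Section 2 says it is unknown how oxygen should be given if it helps, and expects LTOT to be more intrusive than NOT. Section 7 plans to evaluate the two regimens against each other as well as against best medical therapy. If both work, a fixed split could credit one and miss the other because of a threshold that could have been relaxed at no cost in patients.

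**Working it through.** **Inputs.** From section 8.1: difference 10, SD 25, significance level 0.025 per comparison, power 80%, attrition 20%. From section 4.1: three equal arms. Sidedness is not stated; it is inferred in step 1.

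**1. The plan's own figure.** n per arm = 2 × (25/10)² × (z for 0.025 two-sided + z for 80% power)² = 2 × 6.25 × (2.2414 + 0.8416)² = 118.8, so 119. A one-sided 0.025 would give 2 × 6.25 × (1.9600 + 0.8416)² = 98.1, so 99. The plan's figure is therefore two-sided. With attrition, 119/0.8 = 148.75, and 150 × 0.8 = 120 analysed per arm. The 119 and the 150 are sound.

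**2. Set-up for comparing procedures.** With 120 per arm, the standard error of a difference is 25 × √(2/120) = 3.227, and a true 10 points gives an expected z of 10/3.227 = 3.098. The shared control arm with equal allocation gives a correlation of 0.5 between the two z statistics. Rejection probabilities come from the bivariate normal distribution with these critical values:
- Bonferroni: 2.2414 for both tests.
- Holm: 2.2414 for the larger |z|, then 1.9600 for the other.
- Step-down Dunnett: 2.212 (equivalent to 0.0270), then 1.9600.

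**3. Results at 120 per arm, unadjusted SD 25.**

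| True benefit | Quantity | Bonferroni | Holm | Step-down Dunnett |
|---|---|---|---|---|
| 10 and 10 | Power per comparison | 80.4% | 84.9% | 85.3% |
| 10 and 10 | Power to show both | 69.3% | 78.3% | 78.5% |
| 10 and 10 | Power for at least one | 91.6% | 91.6% | 92.0% |
| 10 and 0 | Power for the effective regimen | 80.4% | 80.6% | 81.4% |
| 10 and 0 | False declaration of the other | 2.5% | 4.2% | 4.3% |
| 0 and 0 | Familywise error | 4.65% | 4.65% | 5.0% |

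The rows are consistent with one another. When both effects are equal, power per comparison is the mean of at-least-one and both: for Holm, (91.6 + 78.3)/2 = 84.95, and for Bonferroni (91.6 + 69.3)/2 = 80.45, which agree with the table to rounding. In the 10-and-0 row the unrounded Holm gain is about 0.15 points. At exactly 119 per arm the pattern is the same: 80.1% to about 84.6% per comparison, and 68.8% to about 78% for both.

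**4. Effect of baseline adjustment.** The protocol gives no correlation between baseline and one-year scores. If 25 is the SD before adjustment and the correlation is assumed to be 0.5, the residual SD is 25 × √(1 − 0.25) = 21.65. At 0.6 it is 25 × √(1 − 0.36) = 20. With 10 points in both arms:
- Correlation 0.5: per comparison 90.9% to 93.8% (gain 2.9 points); both 84.7% to 90.4% (gain 5.7).
- Correlation 0.6: per comparison 94.9% to 96.8% (gain 1.9); both 91.0% to 94.8% (gain 3.8).

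**5. Intervals.** Holm rejects more than Bonferroni only when the second P lies between 0.025 and 0.05. In each such case the 97.5% interval for that comparison includes zero. With both regimens at 10 points and SD 25, this happens in 78.3 − 69.3 = 9.0% of trials.

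**The case against.** The strongest objection is that the protocol contains no fixed testing rule to criticise. The 0.025 is a sample-size assumption, Holm's first step is also 0.025, and a team planning Holm could have written section 8.1 exactly as it stands. The SAP may already name a procedure. This stands in part. A reader might infer that the protocol commits to a fixed 0.025 for each test and so wastes power; the text does not go that far. It does offer an equal split and nothing else, so Bonferroni is the reading an analyst would reach by default.

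A second objection is that the gain is conditional. The primary question asks about benefit from either regimen, and for finding at least one Holm adds nothing. If only one regimen works, the gain is negligible. Adjustment for baseline, which section 8.2 plans, would reduce the gain further. All of this stands and limits the size of the point.

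A third is that the change is not free. False declaration of an ineffective regimen alongside an effective one rises from 2.5% to about 4.2%, and 97.5% intervals may disagree with the test. Both are true. The first remains within the 5% familywise limit, and the second is a reporting matter to settle in advance. What is free is the sample size.

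**Conclusion.** The point holds as an inexpensive improvement, not as a correction. The equal split is valid and the sample size reproduces. Holm rejects everything that the split rejects and keeps familywise error at or below 5%. If both regimens give 10 points, it adds about 4.5 points of power per comparison and about 9 points for showing both.

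These figures assume a normal approximation, equal SDs of 25, 120 analysed per arm and no gain from baseline adjustment. Under the assumed correlations of 0.5 and 0.6, the gain for showing both falls to 5.7 and 3.8 points.

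A reader might infer that the trial is too large. It is not: with Holm, about 107 per arm would give 80% per comparison if both regimens work, but about 119 are still needed if only one does. Nor is step-down Dunnett the same procedure as Holm. It uses the 0.5 correlation, spends the full 5% and is slightly more powerful.

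**What to change.** Add to section 8.2, or to the SAP, before results are seen: the two primary comparisons, LTOT and NOT each against best medical therapy, are tested by Holm's procedure at a two-sided familywise 5%; the smaller P value is compared with 0.025 and, if it is significant, the other with 0.05.

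State also which confidence intervals will be reported, that the Holm decision governs significance, and that a 97.5% interval may include zero for a second comparison that Holm rejects. Acknowledge that, if only one regimen works, the chance of falsely declaring the other is about 4.2% instead of 2.5%. Step-down Dunnett may be named instead if the small extra power is wanted.

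Keep 119 evaluable and 150 randomised per arm. The cost is a few lines of text and no patients.
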